#### Percentage area reduction from baseline

The percent change in the surface area of the Index Ulcer (PAR) will be calculated using the following formula:

((A1-A2)/A1)\*100

Where A1 is the baseline area (at randomization), and A2 is the area at the specified time point.

#### Statistical methodology

#### Missing data

\*For calculation purposes, days to healing = date ulcer is first healed – date of randomization.

SAP: LLA-Nu3-CLIN002 Page 6 of 21

Missing data may be the result of missed visits, subjects lost to follow-up or who have died, and may be endpoint data or covariate data. Missing continuous outcome data will be imputed in this study using the LOCF (last observation carried forward). If wound healing outcomes are missing these will be imputed as follows: (a) If an event removes the index ulcer, such as an amputation, the outcome will be scored as not healed; (b) If a subject dies, the outcome will be scored as not healed; (c) If a subject is withdrawn from the study, the outcome will be scored as not healed; and (d) for all remaining non-healed index ulcers in the drug groups, the outcomes will be based on non-right-censored outcomes in the SOC group to weight outcomes.

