## **Patient Populations**

The populations defined for the final analysis include intent-to-treat (ITT), modified-intent-to-treat (MITT), per protocol (PP), and safety populations are defined as shown in Table 2. All the defined populations will be analyzed unless the populations are the same; for example, if no subjects were withdrawn, lost to follow-up, or died, and all subjects received assigned doses, then the ITT and MITT groups would be identical and MITT analysis would be dropped.

Variable	Intent-to-treat (ITT)	Modified- intent-to-treat (MITT)	Per Protocol (PP)	Safety (SP)
All randomized subjects	✓			
Analysis per assigned treatment group	✓	\		\
Major protocol violation	\	\		\
Withdrawn, died, or lost to follow-up	✓			\
Received at least one treatment	✓	✓		✓
Received at least 80% of doses			✓	
Received no treatment	1			

SAP: LLA-Nu3-CLIN002 Page 5 of 21

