  - Laboratory evaluations and vital signs assessments will be summarized by dose group (including placebo group) and time point of collection (i.e., visit number starting with randomization visit) (see shell Table 2).
    - Tables will also be constructed for each subject per timeline (see Shell Table 3)

[figure not shown]
SAP: LLA-Nu3-CLIN002 Page 8 of 21

 Table describing change in value and percentage change from baseline for each visit will be provided for vital signs for each subject (see Shell Table 4)

- Table describing out-of-normal range shifts will be provided for clinical laboratory results for each subject, grouped according to dose group (See Shell Table 5)
- Table describing changes noted in physical examinations (at each visit after randomization) will be constructed for each subject, grouped according to dose group (see Shell Table 6)
- Efficacy date will be analyzed as follows:
  - Summary statistics of DFUs that healed by treatment group by 6 weeks (numbers and percentage healed); graph showing weekly percentage of wounds healed by treatment group
  - PAR weekly plot by treatment group; summary table of PAR values by week and treatment group
  - Time to heal within 6 weeks (summary time to heal statistics by treatment group) using Kaplan-Meier method; probability of wound healing (1-survival ≡ 1-wounds not healed) plot by treatment group. If the percentage healed figures for the 5% and 10% Nu-3 groups at 6 weeks is within 10% and a statistical power calculation shows that the proportions of wounds healed for the combined versus placebo groups is at least 80%, the times to heal will be tested using the logrank test.
  - Bacterial counts (CFU/g) for weeks 0-4 will be analyzed by (a) reporting the means and standard deviations for each group at each time point and (b) using GLMM (general linear modeling with repeated measures [weeks 1-4] and counts at week 0 as a factor)
  - Microbiological data will be summarized for each of the 3 treatment groups for each visit (visits 1, 3, 4, 5, 6, 7; unscheduled visit; early termination) as follows (a) list of species detected in each microbiological sample (Shell Table 11); and (b) susceptibility testing to the following drugs for each microbiological sample: penicillin, vancomycin, and linezolid (Shell Table 12)
    - \*A reason will be given in each instance in which susceptibility testing was *not* done (e.g., no growth).

SAP: LLA-Nu3-CLIN002 Page 9 of 21

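### In the ITT summaries, LOCF carries the last ulcer-area result past amputation, death or withdrawal without a final image, and counts it as observed

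*SAP*

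**What the plan says.** The SAP, Missing data, gives one rule for continuous outcomes: "Missing continuous outcome data will be imputed in this study using the LOCF (last observation carried forward". It does not distinguish a missed visit from an amputation or a death.

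The same paragraph handles missing healing outcomes by reason:
- removal of the ulcer: "a) If an event removes the index ulcer, such as an amputation, the outcome will be scored as not healed"
- death: "b) If a subject dies, the outcome will be scored as not healed"
- withdrawal: "c) If a subject is withdrawn from the study, the outcome will be scored as not healed"

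PAR is defined in the SAP under Percentage area reduction from baseline as ((A1-A2)/A1)*100: "Where A1 is the baseline area (at randomization), and A2 is the area at the specified time point". It is reported as "PAR weekly plot by treatment group; summary table of PAR values by week and treatment group", with no test attached.

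Under Patient Populations, "All the defined populations will be analyzed unless the populations are the same". As the population table reads, subjects who withdrew, died or were lost are kept in ITT and the safety population and left out of MITT and PP.

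Protocol section 8 asks for an early-termination visit that includes imaging of the ulcer. Protocol section 10.1 keeps subjects who stop treatment only in the visit schedule. No section sets an area or PAR after amputation or death, and no PAR sensitivity analysis is described.

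**The concern.** PAR needs an area at the stated time point. After amputation of the ulcer site, or after death, there is no ulcer to measure. LOCF supplies an area anyway and repeats it to the last visit. If the ulcer had been shrinking, the PAR table continues to show that shrinkage for a subject whom healing rules (a) and (b) count as a failure. A subject who withdraws and has no early-termination image is carried forward in the same way.

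The carried values also enter the table as if they had been measured. The weekly n then overstates how many ulcers were imaged, and so do the 95% limits for the mean that the protocol synopsis lists among its descriptive statistics.

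Ulcer surface area is a named secondary variable, and after Cohort 2 the DMC reviews all the data to recommend a dose. With 12, 12 and 8 subjects per reported group, one carried value is visible in a group mean.

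**Working it through.** The plan states no missing-data rate, PAR effect or SD, so there is no figure to reproduce except the group sizes: 2 cohorts x (12 + 4) = 32, giving 12 on 5%, 12 on 10% and 4 + 4 = 8 on placebo when pooled, as in the SAP shell tables.

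**Step 1: apply the rules to one subject.** Assume an ulcer of 5 cm² at baseline and 2 cm² at the last image, then amputation or death.
- PAR at last image = (5 - 2)/5 x 100 = 60%.
- Healing outcome: not healed.
- PAR at each later visit in ITT: 60%.

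**Step 2: shift in a group mean.** With k affected subjects, last PAR L and group size n, LOCF differs from scoring those subjects as no reduction (PAR 0) by k x L / n.
- One subject, L = 40: 40/12 = 3.3 points; 40/8 = 5.0 points.

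Range over assumed inputs:

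| Affected | L = -20% | L = 20% | L = 40% | L = 60% | L = 80% |
|---|---|---|---|---|---|
| 1 of 12 | -1.7 | 1.7 | 3.3 | 5.0 | 6.7 |
| 2 of 12 | -3.3 | 3.3 | 6.7 | 10.0 | 13.3 |
| 1 of 8 | -2.5 | 2.5 | 5.0 | 7.5 | 10.0 |
| 2 of 8 | -5.0 | 5.0 | 10.0 | 15.0 | 20.0 |

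The first column shows that an enlarging ulcer pulls the mean down.

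**Step 3: the opposite case.** A dropout last seen at 40% whose ulcer would have reached 80% lowers a mean of 12 by (80 - 40)/12 = 3.3 points.

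**Step 4: do the other populations bracket the answer?** Take the subject of Step 1, with everyone else in the group at 40%.
- ITT with LOCF: (11 x 40 + 60)/12 = 41.7%; in a group of 8, (7 x 40 + 60)/8 = 42.5%.
- Subject left out, as in MITT or PP: 40.0% in both.
- Failure scored as PAR 0: 440/12 = 36.7%; 280/8 = 35.0%.

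In this example both planned results lie above the one that counts the event as a failure, by 5.0 and 3.3 points (n = 12) or 7.5 and 5.0 points (n = 8).

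**Step 5: amputation recorded as zero.** If a site enters 0 cm² after amputation, PAR = (5 - 0)/5 x 100 = 100%, the same as a healed ulcer. The SAP does not exclude this entry.

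**The case against.** The strongest reply is that the outputs are descriptive in a pilot, and that much protection is already planned.
- MITT and PP, as the table reads, leave out subjects who withdrew, died or were lost. This stands in part. Step 4 shows that leaving failures out is not the same as counting them, and a subject with an amputation who stays in the study could remain in MITT.
- The early-termination image, when obtained, is the value carried and may record the worsening. This stands for withdrawals. It does not help after death, after removal of the ulcer, or when that visit is missed.
- The CONSORT flow chart, the withdrawal listing by group and week, and the check on missing data show attrition. This stands, but none of them puts the number measured beside each weekly PAR.
- LOCF is harmless for healed ulcers, because it carries an area of 0. This stands, and the fix must preserve it.

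A reader might infer more than the documents support:
- **That the two rules score the same failure in opposite ways.** They do not. Healing means complete epithelialization, so a completer measured at +40% is also not healed.
- **That LOCF always flatters PAR.** It carries whatever was last seen (Steps 2 and 3).
- **That the SDs are too small.** This is not shown; a frozen value can widen the spread when other ulcers keep shrinking. What can be said is that n is overstated.
- **That the shift is larger still.** Comparing +40% with a doubled area (-100%) gives 140/12 = 11.7 points, but nothing in the documents supports that comparator.
- **That a mixed model without imputation cures the problem.** It does not score amputation or death as failure; it projects from the same earlier values under a missing-at-random assumption.

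**Conclusion.** The concern holds within limits. As written, the SAP assigns an ulcer area in ITT after the ulcer or the subject is gone, and carries the last PAR for withdrawals with no final image. No other rule overrides this. The direction is not fixed.

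The size, 3.3 points (n = 12) or 5.0 points (n = 8) for one subject, rests on an assumed last PAR of +40% and a comparison with PAR 0. How often it would occur cannot be judged from the documents, and few such events may occur in a trial limited to Wagner grade 1, noninfected, adequately perfused ulcers. No p-value and no primary safety result depends on it. What is affected is the reading of weekly means and plots in small groups, which form part of the data behind the dose recommendation.

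**What to change.** Amend the SAP's Missing data and Analysis sections before database lock:
1. Make the main weekly PAR summary observed values, with the number measured at each visit.
2. Set healed ulcers to area 0 (PAR 100%) at later visits. The Brief Trial Description suggests that visits may stop at healing, so an observed-only table would otherwise lose the successes.
3. After amputation of the ulcer site or death, treat PAR as a failure: assign the worst rank and report medians with IQR, in line with healing rules (a) and (b). State that area is never entered as 0 after amputation.
4. For withdrawals, use the early-termination image at the visit window it falls in, and show later visits as missing in the n.
5. Keep LOCF only as a sensitivity summary, labelled as such.

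A repeated-measures mixed model is optional and does not replace item 3. The cost is SAP wording and minor programming; the SAP already provides medians with IQR for non-normal variables. PAR may look slightly less favourable.

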# Days to Index Ulcer healing

For subjects who achieve healing of index ulcer during the Treatment Phase, days to healing of Index Ulcer will be calculated. Time to first assessment of ulcer healing will be used for this time-to-event analysis.\*

For the right censored subjects (i.e., subjects who do not have a wound healing event) the time to heal in days will be:

- 42 days if the subject completes the study
- Time of the early termination date of randomization for those subjects who withdraw or terminate early from the study (i.e. the censored time)

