#### Research hypotheses

Because this trial is focused on safety, no primary research hypotheses (hypotheses tested using statistical tests) will be tested. However, two secondary endpoints will be tested statistically, one of which has to meet a priori conditions to decide validity of testing.

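### The residual rule for missing healing outcomes covers only the drug groups and borrows from an undefined SOC group, so placebo has no rule for the same case

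*SAP*

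**What the plan says.** The SAP's Missing data section opens its healing rules with "If wound healing outcomes are missing these will be imputed as follows". Rules (a) ulcer removed, (b) death and (c) withdrawal all score the outcome as not healed and name no arm, so they apply to everyone; rule (c), for example, reads "If a subject is withdrawn from the study, the outcome will be scored as not healed". Rule (d) takes the remainder: for "non-healed index ulcers in the drug groups, the outcomes will be based on non-right-censored outcomes in the SOC group to weight outcomes".

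Three other places bear on how (d) works:

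- SAP, Days to Index Ulcer healing, describes "right censored subjects (i.e., subjects who do not have a wound healing event" and sets their time at "42 days if the subject completes the study", or at early termination.
- SAP, Analysis (efficacy), reports the percentage healed by group at 6 weeks and a Kaplan-Meier analysis. It allows a log-rank test only if the two Nu-3 groups are within 10% of each other in percentage healed and a power calculation for combined Nu-3 against placebo reaches at least 80%. SAP, Research hypotheses, says "two secondary endpoints will be tested statistically, one of which has to meet a priori conditions to decide validity of testing".
- SAP, Brief Trial Description, and Protocol 5.1 give standard of care to both the Nu-3 and the placebo arms.

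**The concern.** Rule (d) handles the arms differently. A Nu-3 subject whose healing outcome is missing for a residual reason gets an imputed value. A placebo subject in the same position gets none: last observation carried forward is limited to continuous outcomes, and the censoring section gives times, not a healed or not-healed value.

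The donor is also unclear. There is no arm called the SOC group, and the weighting operation is not described. By the SAP's own definition, right-censored means no healing event, so outcomes that are not right-censored are healed outcomes. Taken literally, drug-arm ulcers would be imputed from healed controls only, which can push the healed percentage in one direction, towards Nu-3. The wording about weighting fits better with using the observed placebo healing rate, but the text does not say so. Two programmers could reasonably produce different results.

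An imputed healing also has no date. The same subject could count as healed in the 6-week percentage and as censored in the Kaplan-Meier curve.

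At stake are the secondary 6-week healed percentages and, in principle, the conditions for the log-rank test.

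**Working it through.** There is no stated figure to reproduce; the SAP does no sample size calculation. The allocation agrees: 2 cohorts × 16 = 32, and 3:1 gives 24 active and 8 placebo, with 12 per dose group.

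**Who falls under (d).** Ulcer removal, death and withdrawal go to (a)–(c). Protocol 10.3 treats loss to follow-up as withdrawal, which would send it to (c). What remains is mainly a subject still in the study without a usable Day 42 assessment; the protocol has no visit between Day 28 and Day 42. The SAP lists loss to follow-up separately from withdrawal (Patient Populations; Analysis), so more subjects could fall under (d).

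**Assumptions (not in the documents).** k = 0 to 3 of 24 drug outcomes fall under (d), so m = k/24; the same share m is missing in placebo; true healing p is the same in both arms, 10 to 40%. Any difference between the arms is then spurious.

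| Reading of (d) | Missing placebo outcomes | Drug minus placebo | k = 1 to 3 |
|---|---|---|---|
| Literal: drug = (1−m)p + m | left out: placebo = p | m(1−p) | 2.5 to 11.3 points |
| Literal | scored not healed: placebo = (1−m)p | m | 4.2 to 12.5 points |
| Placebo rate: drug = p | left out | 0 | 0 |
| Placebo rate | scored not healed | mp | 0.4 to 5.0 points |

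The ends of the ranges are (1/24)(0.6) = 2.5 and (3/24)(0.9) = 11.3; 1/24 = 4.2 and 3/24 = 12.5; (1/24)(0.1) = 0.4 and (3/24)(0.4) = 5.0. With k = 0 every row is 0.

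**Worked example (assumed counts).** Observed healed 9/24 Nu-3 and 2/8 placebo; 3 Nu-3 and 1 placebo outcome missing.

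- Not healed in all arms: 37.5% v 25.0%, difference 12.5 points.
- Placebo rate 2/7 for the drug arm, missing placebo not healed: (9 + 3 × 2/7)/24 = 41.1% v 25.0%, difference 16.1.
- Literal, missing placebo not healed: 12/24 = 50.0% v 25.0%, difference 25.0.
- Literal, missing placebo left out: 50.0% v 2/7 = 28.6%, difference 21.4.

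**Mismatch with Kaplan-Meier.** One whole imputed healing is 1/12 = 8.3 points in a dose group, if nobody is censored earlier. If the outcome is weighted by a placebo rate of 10 to 40%, the shift is 8.3 × 0.1 to 0.4 = 0.8 to 3.3 points.

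**Log-rank decision.** Let X ~ Bin(12, p_d), Y ~ Bin(11, p_d) with one outcome missing in the second dose group, and C ~ Bin(8, p_p). The test is run if the two dose groups differ by at most 1 ulcer of 12 (8.3 points; 2 of 12 is 16.7 and fails) and power for (X+Y)/24 v C/8 is at least 80% (two-sided 0.05, normal approximation). The table gives the share of trials in which scoring the missing outcome healed rather than not healed changes the decision. The SAP names no power formula, so both variance forms are shown.

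| True healing, Nu-3 v placebo | Pooled variance | Unpooled variance |
|---|---|---|
| Equal, 10, 20, 30, 40% | 0.12, 0.26, 0.33, 0.42% | 1.10, 2.71, 1.71, 1.05% |
| 45 v 25% | 1.7% | 4.3% |
| 60 v 20% | 9.2% | 12.8% |
| 50 v 10% | 9.4% | 15.6% |

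**The case against.** The upper figures need healed-only donors. If every donor is healed there is nothing to weight, so the author of the SAP probably meant the placebo rate, and the SOC group, set against the drug groups, can hardly be anything but placebo plus SOC. On that reading the distortion is 0 to 5.0 points, and exactly 0 if missing placebo outcomes are left out. Much of this stands: the placebo-rate reading is the more natural one. But it remains an inference, and even then the result depends on a placebo rule that the SAP does not contain.

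Reach is small. Healing is dated at first assessment, so earlier healers are not missing, and zero subjects under (d) is quite possible. This also stands.

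The log-rank calculation varies a drug outcome with all placebo outcomes observed, so it measures fragility in a small trial more than unequal handling. That is fair. Repeating it with one placebo outcome missing instead gives 0.6 to 0.7% under equal healing (pooled variance), still negligible.

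The SAP gives censoring times only for completers and early terminators, and a subject lacking a Day 42 assessment is not clearly either. This leaves the censoring time open, but such a subject still has no healing event and so cannot count as healed in the Kaplan-Meier analysis.

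Finally, this is a safety pilot with no primary hypothesis test. That limits the severity; it does not justify treating the arms differently.

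**Conclusion.** The concern holds. Rule (d) gives a missing outcome a value in the Nu-3 groups and none in placebo, from a donor group that the SAP does not define. On the assumptions above, 1 to 3 affected drug subjects produce a spurious Nu-3 advantage of 2.5 to 12.5 points on the literal reading and 0 to 5.0 points on the placebo-rate reading; with none affected there is no effect. The missing counts and healing rates are assumed, and the power figures are approximate with 8 placebo subjects. The log-rank decision is rarely altered except when the true effect is around 40 points. The primary safety endpoint is not affected. This is at the low end of what should be fixed: small reach, but unequal handling of the arms that a wording change removes. Confidence is medium, mainly because the number of subjects who will fall under (d) is unknown.

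**What to change.** Before unblinding, replace (d) with one rule for all arms that extends (a)–(c): an index ulcer not documented as healed by 6 weeks counts as not healed; no observed outcome is replaced; the number missing is reported per arm. Keep the Kaplan-Meier analysis as the SAP defines it, with completers censored at 42 days and early terminators at termination. If censoring at the last assessment is wanted as a sensitivity analysis, state it as an addition.

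The cost is SAP wording and slightly conservative healed percentages. With equal shares missing, a true 20-point effect reads 20 × (1−m) = 19.2, 18.3 or 17.5 points for k = 1, 2 or 3, and no effect still reads zero. If missing shares differ by arm, a shift of p × (placebo share − drug share) remains under no effect: +0.8 to +3.3 points at 1/24 drug v 1/8 placebo, and −1.3 to −5.0 points at 3/24 v 0/8.

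If control-based imputation was intended, that is an acceptable alternative: name the placebo group, define donors as all observed placebo outcomes (healed and not healed), and apply the same rule to missing placebo outcomes. With equal shares missing it dilutes a true effect by the same amount, and it leaves no expected shift under no effect.

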#### Data QC

- 1. Inspect for accuracy of input:
  - a. Plausible values
  - b. Outliers or out-of-range values
- 2. Evaluate degree and distribution of missing data; for non-endpoint data query PERI
- 3. Identify non-normal continuous variables and outliers; data for non-normal variables will include median/IQR.

# **Statistical Analysis**

Analysis will be started once database lock for the trial is initiated and the final version of the SAP is released in Lakewood-Amedex' system.

#### Research hypotheses

Because this trial is focused on safety, no primary research hypotheses (hypotheses tested using statistical tests) will be tested. However, two secondary endpoints will be tested statistically, one of which has to meet a priori conditions to decide validity of testing.

# **Analysis**

The following analyses will be conducted:

- Flow chart (subjects) with disposition according to CONSORT criteria. (see shell Figure 1).
- Overall trial statistics (enrollment dates, site numbers, numbers of subjects, group assignments)
- Withdrawals (including death), and loss to follow-up (total and by group assignment) with week of discontinuation and reason.
- Screen failure rate and screen failure reasons according to exclusion criteria

SAP: LLA-Nu3-CLIN002 Page 7 of 21

Demographics between groups at baseline (subject-related and wound-related variables): patient age, smoking/alcohol status, BMI, HbA1c, creatinine levels; diabetes duration); number of concurrent DFUs, prior DFUs and amputations, history of DFU recurrence, history of and significant foot deformities (if available); DFU location, ulcer duration, initial area; baseline variables between groups will be tested using t tests, Mann-Whitney, chi square, and Fisher exact tests (as appropriate) without adjustment for multiplicity testing (see shell Tables 1 and 7).

- Subject comorbidities will be listed using first-level medDRA organ classes by treatment group (see shell Table 8); for each subject the total number of comorbidities will be calculated and then the means between groups will be tested in the same way as for demographics and added to shell Table 1
- Prescription medications will be listed using WHODrug classes by treatment group (see shell Table 9); for each subject the total number of prescription drugs will be calculated and then the means between groups will be tested in the same way as for demographics and added to shell Table 1
- The primary endpoint analysis will be a summary of the incidence of treatmentemergent adverse events (TEAEs), including subject and overall AE rates by treatment group:
  - Summary statistics for each treatment group (count of TEAEs per group/per patient; summary rates per group; notes of unexpected occurrences during the study; relevant decisions made) [text in report]
  - SAE (brief description; resolution; impact on study (e.g., withdrawal, etc.) [text in report]
  - All TEAEs by system organ class (SOC), preferred term (PT), severity, and relationship to test article (see shell Table 10).
- Other safety data will be analyzed as follows:
  - Laboratory evaluations and vital signs assessments will be summarized by dose group (including placebo group) and time point of collection (i.e., visit number starting with randomization visit) (see shell Table 2).
    - Tables will also be constructed for each subject per timeline (see Shell Table 3)

[figure not shown]
SAP: LLA-Nu3-CLIN002 Page 8 of 21

 Table describing change in value and percentage change from baseline for each visit will be provided for vital signs for each subject (see Shell Table 4)

- Table describing out-of-normal range shifts will be provided for clinical laboratory results for each subject, grouped according to dose group (See Shell Table 5)
- Table describing changes noted in physical examinations (at each visit after randomization) will be constructed for each subject, grouped according to dose group (see Shell Table 6)
- Efficacy date will be analyzed as follows:
  - Summary statistics of DFUs that healed by treatment group by 6 weeks (numbers and percentage healed); graph showing weekly percentage of wounds healed by treatment group
  - PAR weekly plot by treatment group; summary table of PAR values by week and treatment group
  - Time to heal within 6 weeks (summary time to heal statistics by treatment group) using Kaplan-Meier method; probability of wound healing (1-survival ≡ 1-wounds not healed) plot by treatment group. If the percentage healed figures for the 5% and 10% Nu-3 groups at 6 weeks is within 10% and a statistical power calculation shows that the proportions of wounds healed for the combined versus placebo groups is at least 80%, the times to heal will be tested using the logrank test.
  - Bacterial counts (CFU/g) for weeks 0-4 will be analyzed by (a) reporting the means and standard deviations for each group at each time point and (b) using GLMM (general linear modeling with repeated measures [weeks 1-4] and counts at week 0 as a factor)
  - Microbiological data will be summarized for each of the 3 treatment groups for each visit (visits 1, 3, 4, 5, 6, 7; unscheduled visit; early termination) as follows (a) list of species detected in each microbiological sample (Shell Table 11); and (b) susceptibility testing to the following drugs for each microbiological sample: penicillin, vancomycin, and linezolid (Shell Table 12)
    - \*A reason will be given in each instance in which susceptibility testing was *not* done (e.g., no growth).

SAP: LLA-Nu3-CLIN002 Page 9 of 21

Shell Figure 1. Note: Nu-3 = bisphosphocin Nu-3

SAP: LLA-Nu3-CLIN002 Page 10 of 21

Shell Table 1. Patient-related variables by treatment group. Figures in parentheses will be percentage for categorical variables and standard deviation (SD) of the mean for continuous variables; for key variables, such as initial wound area, medians and interquartile ranges (IQR) will be added. p values will have 2 significant figures

Variable	Nu-3 (5%)	Nu-3 (10%)	Placebo	р
Age (years)	xx.x (x.xx)	xx.x (x.xx)	xx.x (x.xx)	0.xx
Race				
Caucasian	x (x)	x (x)	x (x)	
African American	x (x)	x (x)	x (x)	0.xx
Hispanic	x (x)	x (x)	x (x)	
Gender				
Male	x (x)	x (x)	x (x)	0.xx
Female	x (x)	x (x)	x (x)	
Diabetes duration (years)	xx (x.xx)	xx (x.xx)	xx (x.xx)	0.xx
BMI	xx.x (x.xx)	xx.x (x.xx)	xx.x (x.xx)	0.xx
HbA1c	xx.x (x.xx)	xx.x (x.xx)	xx.x (x.xx)	0.xx
Creatinine	xx.x (x.xx)	xx.x (x.xx)	xx.x (x.xx)	0.xx
Comorbidity count	xx.x (x.xx)	xx.x (x.xx)	xx.x (x.xx)	0.xx
Prescription medication	xx.x (x.xx)	xx.x (x.xx)	xx.x (x.xx)	0.xx
count				

Nu-3: bisphosphocin Nu-3 gel

SAP: LLA-Nu3-CLIN002 Page 11 of 21

Shell Table 2. Laboratory evaluations and vital signs assessments by treatment group and visit number; randomization visit=1.

Analyte or Vital Signs	Nu-3 (5%)	Nu-3 (10%)	Placebo
Visit			
Statistic			
<analyte (unit)=""></analyte>			
Visit 1			
n	xx	XX	XX
Mean (SD)	xx.x (xx.xx)	xx.x (xx.xx)	xx.x (xx.xx)
Median (IQR)	xx.x (xx.xx)	xx.x (xx.xx)	xx.x (xx.xx)
Visit 2			
n	XX	XX	XX
Mean (SD)	xx.x (xx.xx)	xx.x (xx.xx)	xx.x (xx.xx)
Median (IQR)	xx.x (xx.xx)	xx.x (xx.xx)	xx.x (xx.xx)
{Continue for all scheduled			
post-randomization visits and			
all analytes. Start a new page			
for every additional analyte}			
<vital (unit)="" sign=""></vital>			
Visit 1			
n	XX	XX	XX
Mean (SD)	xx.x (xx.xx)	xx.x (xx.xx)	xx.x (xx.xx)
Median (IQR)	xx.x (xx.xx)	xx.x (xx.xx)	xx.x (xx.xx)
Continue for all scheduled			
post-randomization visits and			
all vital signs. Start a new page			
for every additional vital sign}			

Nu-3: bisphosphocin Nu-3 gel

SAP: LLA-Nu3-CLIN002 Page 12 of 21

Shell Table 3. Laboratory evaluations and vital signs assessments for each subject by treatment group and visit number; randomization visit=1.

Analyte or Vital Signs	Nu-3 (5%)	Nu-3 (10%)	Placebo
Visit			
Statistic			
Subject ID	XX-XXX	XX-XXX	XX-XXX
<analyte (unit)=""></analyte>			
Visit 1			
Value	xx.x	xx.x	xx.x
Subject ID	XX-XXX	XX-XXX	XX-XXX
<analyte (unit)=""></analyte>			
Visit 2			
Value	XX.X	XX.X	XX.X
{Continue for all scheduled			
post-baseline visits and all			
analytes. Start a new page for			
every additional analyte}			
Subject ID	XX-XXX	XX-XXX	XX-XXX
<vital (unit)="" sign*=""></vital>			
Visit 1			
Value	XX.X	XX.X	xx.x
Subject ID	XX-XXX	XX-XXX	XX-XXX
<vital (unit)="" sign=""></vital>			
Visit 2			
Value	XX.X	xx.x	XX.X
{Continue for all scheduled			
post-baseline visits and all			
vital signs. Start a new page			
for every additional vital sign}			

Nu-3: bisphosphocin Nu-3 gel; \*some vital signs will be paired—for example, blood pressure

SAP: LLA-Nu3-CLIN002 Page 13 of 21

Shell Table 4. Changes in vital signs assessments for each subject by treatment group and visit number compared to randomization visit [1].

Vital Signs Visit	Nu-3 (5%)	Nu-3 (10%)	Placebo
Statistic			
Subject ID	XX-XXX	XX-XXX	XX-XXX
<vital (unit)="" sign*=""></vital>			
<visit 1,="" value=""></visit>	XX.X	xx.x	XX.X
<visit 2,="" change="" in="" sign="" vital=""></visit>	(-) xx.x	(-) xx.x	(-) xx.x
<visit 2,="" change="" in<="" percentage="" td="">(-) xx.x%	(-) xx.x%	(-) xx.x%	</visit>	(-) xx.x%	(-) xx.x%	(-) xx.x%
vital sign>			
{Continue for all scheduled			
post-baseline visits and all			
vital sign changes.}			
{Continue for all scheduled			
post-baseline visits and all			
vital signs. Start a new page			
for every additional vital sign}			

Nu-3: bisphosphocin Nu-3 gel; \*some vital signs will be paired—for example, blood pressure

SAP: LLA-Nu3-CLIN002 Page 14 of 21

Shell Table 5. Out of normal range shifts for laboratory evaluations for each subject by treatment group and visit number; randomization visit=1.

Analyte Visit	Nu-3 (5%)	Nu-3 (10%)	Placebo
Statistic			
Subject ID	XX-XXX	XX-XXX	XX-XXX
<analyte (unit=""></analyte>	70.700		7017001
Visit 1			
Missing	Y/N	Y/N	Y/N
Low	y/N	Y/N	, Y/N
Normal	y/N	Y/N	y/N
High	Y/N	Y/N	Y/N
Subject ID	XX-XXX	XX-XXX	XX-XXX
<analyte (unit=""></analyte>			
Visit 2			
Missing	Y/N	Y/N	Y/N
Low	Y/N	Y/N	Y/N
Normal	Y/N	Y/N	Y/N
High	Y/N	Y/N	Y/N
{Continue for all scheduled			
post-baseline visits and all			
analytes. Start a new page for			
every additional analyte}			

Nu-3: bisphosphocin Nu-3 gel

SAP: LLA-Nu3-CLIN002 Page 15 of 21

Shell Table 6. Changes noted in physical examinations for each subject by treatment group and visit number; randomization visit=1. If there is no change, entry will be blank.

Physical Exam Change Visit	Nu-3 (5%)	Nu-3 (10%)	Placebo
Description			
Subject ID	XX-XXX	XX-XXX	XX-XXX
Visit 1*			
System organ class	Text	Text	Text
Preferred term(s)			
Subject ID	XX-XXX	XX-XXX	XX-XXX
Visit 2			
System organ class	Text	Text	Text
Preferred term(s)			
{Continue for all scheduled			
post-baseline visits and all			
analytes. Start a new page for			
every additional subject}			

Nu-3: bisphosphocin Nu-3 gel; \*Change from last screening visit

SAP: LLA-Nu3-CLIN002 Page 16 of 21

Shell Table 7 (wound-related variables). Figures in parentheses will be percentage for categorical variables and standard deviation (SD) of the mean for continuous variables; for variables that have a non-normal distribution of values, such as initial wound area, medians and interquartile ranges (IQR) will be added.

Variable	Nu-3 (5%)	Nu-3 (10%)	Placebo
Wound area (cm  )	xx.x (x.xx)	xx.x (x.xx)	xx.x (x.xx)
	xx.x (x.xx)	xx.x (x.xx)	xx.x (x.xx)
Wound age (weeks)	xx.x (x.xx)	xx.x (x.xx)	xx.x (x.xx)
	xx.x (x.xx)	xx.x (x.xx)	xx.x (x.xx)
Number of prior DFUs			
0	xx (xx)	xx (xx)	xx (xx)
1	xx (xx)	xx (xx)	xx (xx)
2	xx (xx)	xx (xx)	xx (xx)
≥3	xx (xx)	xx (xx)	xx (xx)
Number of concurrent			
DFUs			
0	xx (xx)	xx (xx)	xx (xx)
1	xx (xx)	xx (xx)	xx (xx)
2	xx (xx)	xx (xx)	xx (xx)
≥3	xx (xx)	xx (xx)	xx (xx)
History of ulcer	xx (xx)	xx (xx)	xx (xx)
recurrence			
Prior amputation	xx (xx)	xx (xx)	xx (xx)
history (extremity,			
amputation type)			
Significant foot	xx (xx)	xx (xx)	xx (xx)
deformity history			
DFU location			
Plantar	xx (xx)	xx (xx)	xx (xx)
Dorsal	xx (xx)	xx (xx)	xx (xx)
DFU location			
Toe	xx (xx)	xx (xx)	xx (xx)
Forefoot	xx (xx)	xx (xx)	xx (xx)
Midfoot	xx (xx)	xx (xx)	xx (xx)
Heel	xx (xx)	xx (xx)	xx (xx)
Ankle	xx (xx)	xx (xx)	xx (xx)
Number of	x (x)	x (x)	x (x)
debridements			

Nu-3: bisphosphocin Nu-3 gel

SAP: LLA-Nu3-CLIN002 Page 17 of 21

Shell Table 8. Comorbidities noted at first physical examination for each subject by treatment group.

Physical Exam Change	Nu-3 (5%)	Nu-3 (10%)	Placebo
Visit			
Description			
Subject ID	XX-XXX	XX-XXX	XX-XXX
System organ class	Text	Text	Text
Preferred term(s)			
Comorbidity count	xx	xx	xx
{Continue for all subjects.			
Start a new page for every			
additional subject}			

Nu-3: bisphosphocin Nu-3 gel; \*Change from last screening visit

SAP: LLA-Nu3-CLIN002 Page 18 of 21

Shell Table 9. Prescription medications noted at first examination for each subject by treatment group.

Physical Exam Change	Nu-3 (5%)	Nu-3 (10%)	Placebo
Visit			
Description			
Subject ID	XX-XXX	XX-XXX	XX-XXX
Drug class	Text	Text	Text
Preferred term(s)			
Prescription count	XX	XX	XX
{Continue for all subjects.			
Start a new page for every			
additional subject}			

Nu-3: bisphosphocin Nu-3 gel; \*Change from last screening visit

SAP: LLA-Nu3-CLIN002 Page 19 of 21

Shell Table 10. Categorization of AEs by medDRA terms, severity, and relatedness.

TEAE Category	Nu-3 (5%)	Nu-3 (10%)	Placebo
System organ class			
List of classes			
Preferred term(s)	xx (xx)	xx (xx)	xx (xx)
{Continue for all system organ			
classes. Start a new page for each			
new system class as needed}			
Severity			
1	xx (xx)	xx (xx)	xx (xx)
2	xx (xx)	xx (xx)	xx (xx)
3	xx (xx)	xx (xx)	xx (xx)
4	xx (xx)	xx (xx)	xx (xx)
5	xx (xx)	xx (xx)	xx (xx)
Relatedness			
Not related	xx (xx)	xx (xx)	xx (xx)
Unlikely to be related	xx (xx)	xx (xx)	xx (xx)
Possibly related	xx (xx)	xx (xx)	xx (xx)
Probably related	xx (xx)	xx (xx)	xx (xx)
Definitely related	xx (xx)	xx (xx)	xx (xx)
TOTAL	XX	xx	XX

Nu-3: bisphosphocin Nu-3 gel

SAP: LLA-Nu3-CLIN002 Page 20 of 21

Shell Table 11. Microbiological species identification from wound swabs for each subject by treatment group and visit number; randomization visit=1.

Microbiological Identity	Nu-3 (5%)	Nu-3 (10%)	Placebo
Statistic			
Subject ID	XX-XXX	XX-XXX	XX-XXX
Visit 1			
Species 1	text	text	text
{Continue listing for all species			
identified}			
Subject ID	XX-XXX	XX-XXX	XX-XXX
Visit 3			
Species 1	text	text	text
{Continue listing for all species			
identified}			
{Continue for all visits for			
which data are available. Start			
a new page for every subject			
ID}			

Nu-3: bisphosphocin Nu-3 gel

SAP: LLA-Nu3-CLIN002 Page 21 of 21

Shell Table 12. Microbiological susceptibility testing to penicillin, vancomycin, and linezolid from wound swabs for each subject by treatment group and visit number; randomization visit=1.

Susceptibility Testing Statistic	Nu-3 (5%)	Nu-3 (10%)	Placebo
Subject ID	XX-XXX	XX-XXX	XX-XXX
Visit 1			
<penicillin></penicillin>			
Value*	text	text	text
Interpretation**	text	text	text
- <vancomycin></vancomycin>			
Value	text	text	text
Interpretation	text	text	text
<linezolid></linezolid>			
Value	text	text	text
Interpretation	text	text	text
Subject ID	XX-XXX	XX-XXX	XX-XXX
Visit 3			
<penicillin></penicillin>			
Value	text	text	text
interpretation	text	text	text
<vancomycin></vancomycin>			
Value	text	text	text
Interpretation	text	text	text
<linezolid></linezolid>			
Value	text	text	text
Interpretation	text	text	text
{Continue for all visits for			
which data are available. Start			
a new page for every subject			
ID}			

Nu-3: bisphosphocin Nu-3 gel

\*Values can have a variety of numerical formats; for example, 0.08, <=0.01, >2 (If susceptibility was not done a reason will be substituted instead of a value); \*\*interpretation can only have one of 4 values: susceptible (S), intermediate (I), resistant (R), or not applicable (N).
